Ten (10) health facilities will be selected from two districts in Sindh: Karachi and Thatta. Within those districts, health facilities in urban areas of Karachi and rural areas of Thatta will be approached to participate in the trial. The health facilities will be selected based on 1) the number of DMPA acceptors; 2) availability of both LHV and LHWs; and 3) logistical factors. Table 1 provides a proposed sample of study sites with DMPA client volume from the most recent month of available data. Final selection of districts and health facilities within them will be determined in collaboration with in-country partners, AKU and Jhpiego as more information on the distribution of LHWs and LHV and client volume in Sindh becomes available. The sample, including the number of districts or the number of health facilities and their distribution may be adjusted based on this information. For example, we may add another rural district if sufficient numbers cannot be found that meet criteria for LHW experience, current status (i.e., active, not active) or the health facility's ability or willingness to participate in the trial. Alternatively, more sites may be added within the same districts if client volume or health provider interest in trial participation is low.

Table 1. Proposed health facilities and most recent DMPA client volume data

Facility name	District (location)	Client volume in most recent month available of new and continuing injectable clients*
RHS-A Center, SG Hospital Saudabad	Karachi (urban)	30
FWC, SG Hospital Korangi 5	Karachi (urban)	125
FWC-Shah Faisal Colony No. 1, KMS MCH Center	Karachi (urban)	82
FWC Korangi 33-C, BHU Korangi 33-C	Karachi (urban)	73
RHS-A Center, SG Hospital Ibrahim Hyderi	Karachi (urban)	67
RHS-A Center, DHQ Hospital Makli	Thatta (rural)	32
RSH-A Center, THQ Hospital Mirpur Sakro	Thatta (rural)	19
Rural Health Center, Jherruk	Thatta (rural)	0 
RHS-A Center, THQ Hospital Sujawal	Thatta (rural)	38
RHS-A Center, THQ Hospital Mirpur Bathoro	Thatta (rural)	16

\*Data received 2/20/2017

It is anticipated that this proposed study site will have sufficient clients during the data collection period.

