### *Lady Health Visitors*

LHVs assigned to health facilities that correspond to the catchment areas of these LHWs, and who may in the normal course of their duties serve as their supervisors, will be eligible.

Study logistics, resources and need will determine if LHVs should be included in trainings for DMPA IM, but they will be required to attend trainings on SP, as that method will be new to both health cadres. It is particularly important that LHVs be trained on SP along with LHWs, not only to ensure consistency in training and knowledge for both cadres, but also to enable LHVs’ supervisory obligations to their charges providing SP. Jhpiego will certify that once trained, LHWs and LHVs are proficient in screening, counseling and administration of both forms of DMPA prior to interacting with DMPA clients.

Screening and counseling on the use of either type of DMPA has been simplified by WHO’s decision to employ the same medical eligibility requirements for both IM and SP formulations and to harmonize recommendations for the re-injection schedule and grace period (i.e., 2 weeks before the re-injection date or as late as 4 weeks after). Therefore, the only difference in service delivery will be the injection technique for DMPA IM and SP, as all other elements of method provision remain the same.

LHWs and LHVs selected to participate in the trial should not be the “cream of the crop”. To reflect the real-world context outside a trial setting, any provider who successfully completes Jhpiego’s training should be eligible to participate in the trial. Consent will be sought from LHWs and LHVs to observe their interactions with DMPA clients, including the provision of services, as well as to be interviewed by study staff.

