### Sample size

We require a minimum of 342 DMPA clients randomized to receive care from either the LHV or an LHW (1:1 allocation) for 90% power and 5% significance level to test the non-inferiority hypothesis that LHWs can screen potential DMPA clients for method initiation just as adequately as LHVs with a non-inferiority margin of 7.5%, assuming that both LHVs and LHWs perform at a 95% success rate. In Pakistan, there is usually at least one LHV assigned to a health facility and many more LHWs affiliated with and under the supervision of resident LHVs. Therefore, we will use a 3 to 1 ratio of LHWs to LHVs at each health facility in the trial. The three LHWs will be placed on rotation to cover a three-month enrollment and data collection period in the health facility. Rotations among the three LHWs will be based on their individual availability and schedules; not on their perceived competencies or the preference of facility staff.

In order to meet the desired sample size from LHWs and LHVs, we will select 10 health facilities that provide the most DMPA in Karachi and Thatta districts. These facilities will be distributed between rural and urban areas. For logistical reasons, we plan to obtain the full target sample size of 342 DMPA initiators from the urban health facilities to ensure that adequate analyses can be done with this group. We will recruit additional participants from rural facilities to help assess possible differences in performance between LHVs and LHWs in rural and urban areas. Although, we don't expect these differences to exist, the additional sample size will help us to assess whether differences may be likely to exist. If we can be comfortable that providers in rural and urban areas perform in similar manner, the overall sample size for the analysis may be pooled for an increase in power. Please note, however, that the additional sample size from rural areas will not be adequate for separate analyses by location or to assess rural and urban differences statistically. Rural facilities will likely provide a much lower number of DMPA acceptors in the three-month data collection period, but they will each be selected for their ability to enroll at least 20 new acceptors in that period of time. We will then expect to enroll approximately 100 DMPA acceptors from the rural facilities in the recruitment period for an overall total sample size of approximately 442 for this study.

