#### Randomization procedures

A randomization manager from FHI 360, who is not otherwise involved in the study, will prepare a computerized randomization list using permuted blocks before the start of the study. These envelopes

---

a A total of 342 DMPA acceptors will be distributed among the 5 health facilities in urban Karachi district. On average, about 68 acceptors will be recruited per facility of which half will be assigned to LHWs.

[figure not shown]
will be given to the local PI at AKU who will distribute the envelopes to RAs assigned to study health facilities. These RAs will open the randomization envelopes and inform LHWs or LHV when they have been selected to provide DMPA services (screening, counseling) and which form of DMPA (IM or SP) they will provide after the independent third party verifies the client's eligibility for DMPA use.

Women will be randomized in a 1:1 ratio to proceed with DMPA screening by an LHV or LHW. After the independent staff member confirms the client's eligibility to use DMPA, an identical randomization procedure will be performed to randomize women to receive either DMPA IM or SP. The master randomization list will be maintained at FHI 360 and will not be available to study staff.

Randomization groups will be concealed in sequentially numbered, sealed opaque envelopes (SNOSE). We will instruct study staff never to open an envelope until the participant has given consent to participate in the study, is found to be eligible for the study, and is present for DMPA screening and the subsequent administration of the injectable. These envelopes will be provided to AKU in advance of trial implementation. The opened randomization envelopes will be retained as source documents and will be kept under secure and restricted access to protect the confidentiality of the participants.

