This study is a randomized controlled trial conducted in urban and rural health facilities in Sindh Province, Pakistan, using quantitative methods. The study is limited to participating LHWs, LHV and to their clients who voluntarily and independently accept DMPA as their contraceptive method before study recruitment is initiated. Clients will be randomized to receive treatment from either an LHW or an LHV and will also be randomized to receive DMPA IM or SP to prevent selection biases between these

groups. However, comparisons between these injection techniques will only be considered exploratory, focusing instead on acceptability of and satisfaction with the method as reported by clients as well as provider knowledge and the latter's comparisons of SP and DMPA IM.

III. Target Population & Eligibility

The target population for this study is Lady Health Workers and Lady Health Visitors trained to initiate intramuscular and subcutaneous Depo Provera use, as well as DMPA clients of trained Lady Health Workers and Lady Health Visitors.

Eligibility criteria for the study populations are described in table 1. All participants must be at least 18 years of age and consent to being observed and interviewed by study staff.

Table 1: Eligibility criteria

Lady Health Worker Criteria (n=30)	Lady Health Visitor Criteria (n=10)	DMPA acceptors (n=442)

 • Already trained to provide follow-up DMPA IM injections in their community; • Currently providing services in their community • Willingness and ability to participate in the trial 	
 • Assigned to health facilities that correspond to the catchment areas of the LHWs • Willingness and ability to participate in the trial 	
 • Women who select DMPA as their contraceptive method for the first time or after more than a six-month hiatus • Age 18 to 49 and able to legally consent to participate • Consent to provision of DMPA services from an LHV or a trained LHW. • Willingness and ability to participate in the trial

IV. Sampling Design

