We require a minimum of 342 DMPA clients randomized to receive care from either the LHV or an LHW (1:1 allocation) for 90% power and 5% significance level to test the non-inferiority hypothesis that LHWs can screen potential DMPA clients for method initiation just as adequately as LHVs with a non-inferiority margin of 7.5%, assuming that both LHVs and LHWs perform at a 95% success rate. In Pakistan, there is usually at least one LHV assigned to a health facility and many more LHWs affiliated with and under the supervision of resident LHVs. Therefore, we will use a 3 to 1 ratio of LHWs to LHVs at each health facility in the trial.

For logistical reasons, we plan to obtain the full target sample size of 342 DMPA initiators from the 5 urban health facilities in Karachi to ensure that adequate analyses can be done with this group. We will recruit additional participants (~100) from 5 rural facilities in Thatta to help assess possible differences in performance between LHV and LHWs in rural and urban areas, but the expectation is that there will be no difference. LHWs undergo standardized training in Pakistan. If we can be comfortable that providers in rural and urban areas perform in similar manner, the overall sample size for the analysis may be pooled for an increase in power. The decision whether to pool the data or not will be made during the blind review of the data as described below.

Given the relationship between LHWs and LHV within clinics, we plan to account for the correlations of participant outcomes within providers and providers within clinics in the analysis. We expect that some of these correlations would lead to decreases in power and others to lead to increases in power for within clinic comparisons. Power calculations were not adjusted for these potential correlations as the net effect on power may be offset with each other.

V. General Analytic Considerations

A. Data Sources

A.1 Client exit interview

Client exit interviews measure the study's secondary outcomes of client satisfaction with the method and provider. The exit interview also provides additional information related to appropriate screening such as discussion of side effects, warning/danger signs, advantages and disadvantages of DMPA use with clients. The client exit interview includes questions on the following domains:

1. Sociodemographic characteristics
2. Experiences using contraceptive methods
3. Factors in her decision to use DMPA

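### The stated 90% power for the 342 urban clients rests on negligible between-provider variation, not on the offset of correlations that the plan gives as its reason

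*SAP*

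**What the plan says.** The protocol (Sample size) and SAP section IV both require at least 342 clients, allocated 1:1, for 90% power at a 5% level. The margin is 7.5 points and success is assumed to be 95% in both cadres. All 342 are to come from the five urban clinics.

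On staffing, the protocol says: "Therefore, we will use a 3 to 1 ratio of LHWs to LHVs at each health facility in the trial". On how the LHWs share the work: "Rotations among the three LHWs will be based on their individual availability and schedules". A footnote under Randomization procedures adds: "On average, about 68 acceptors will be recruited per facility of which half will be assigned to LHWs". For the rural sites: "We will then expect to enroll approximately 100 DMPA acceptors from the rural facilities in the recruitment period".

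Both documents recognise correlation within providers and of providers within clinics, and note that some of it lowers power while some raises it. They then set the matter aside: "Power calculations were not adjusted for these potential correlations as the net effect on power may be offset with each other". Neither gives an ICC, a design effect or a calculation.

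SAP VIII fits a logit mixed model with random effects for clinic and for provider within clinic. It expects to pool urban and rural data. If descriptive review shows a difference, it falls back on the urban sites and describes their 342 as powered for the test, with no condition attached.

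**The concern.** An offset requires the two sources of correlation to act on the same contrast with comparable weight. Here they do not. Both cadres work in every clinic, so a clinic effect largely drops out of the LHW-LHV difference. A provider is either an LHW or an LHV, so a provider effect does not drop out, and each urban LHV carries about 34 clients.

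If provider variation is not negligible, the chance of an inconclusive result exceeds the stated 10%, most of all in the urban-only analysis. An inconclusive non-inferiority result could then be read as evidence against LHWs when the cause was lack of power.

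**Working it through.** **Inputs from the documents.** Success p = 0.95 in both arms and margin 0.075. Urban: 171 clients per arm, 5 clinics, 1 LHV and 3 LHWs per clinic, so 34.2 clients per LHV and 11.4 per LHW at equal loads. Rural: about 100 clients in 5 clinics, so 10 per arm per clinic. Pooled: 221 per arm.

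**Assumed, because the documents give none.** Provider ICC (rp) from 0 to 0.05 and clinic ICC (rc) 0 unless stated. At 95% success, rp of 0.005, 0.01, 0.02 and 0.05 corresponds to a between-provider SD of 1.5, 2.2, 3.1 and 4.9 points.

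**Step 1. Reproduce 342.** Use Farrington-Manning with independent clients. The constrained null rates are 0.968 and 0.893, so s0 = √(0.968×0.032 + 0.893×0.107) ≈ 0.355. Under the alternative, s1 = √(2×0.95×0.05) = 0.308.

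- One-sided 5%: n = [(1.645×s0 + 1.282×s1)/0.075]² = 170.4 with unrounded inputs, so 171 per arm and **342** in total.
- The unpooled formula with continuity correction also gives 171 (170.3). The plain unpooled (Wald) formula gives 145.
- One-sided 2.5%: Farrington-Manning gives 212 per arm.

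The documents do not name the planning test, but 342 is a one-sided 5% figure with no clustering allowance.

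**Step 2. Variance of the cadre difference.** With arms balanced within clinic, the clinic effect cancels:

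Var = p(1−p) × [(1 − rp − rc)(1/N₁ + 1/N₂) + rp(Σnᵢ²/N₁² + Σnⱼ²/N₂²)]

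- Urban, equal loads: Σn²/N² is 1/5 for LHVs and 1/15 for LHWs. (1/5 + 1/15)/(2/171) = 22.8, so the variance factor is **R = 1 + 21.8 rp − rc**.
- Pooled, equal LHW split: Σn² per arm over clinics = 5×34.2² + 5×10² = 6348.2. (6348.2/221²)(4/3)/(2/221) = 19.15, so R = 1 + 18.15 rp − rc.

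**Step 3. What a full offset needs.** R ≤ 1 requires rc ≥ 21.8 rp in the urban set. That is rc of 0.11, 0.22 or 0.44 for rp of 0.005, 0.01 or 0.02. Since rp + rc cannot exceed 1, no clinic ICC achieves it once rp exceeds 1/22.8 = 0.044.

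The coefficient depends on the design:

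| Design | Coefficient of rp |
|---|---|
| Urban, 5 clinics, equal loads | 21.8 |
| Urban, assumed 20/10/4 split among LHWs | 23.7 |
| Urban, recruitment in proportion to protocol Table 1 (30 to 125 clients) | 25.5 |
| Urban, both | 27.8 |
| Urban, 6 or 8 clinics, equal loads | 18.0 or 13.3 |
| Pooled, equal loads | 18.1 |
| Pooled, both kinds of uneven load | 22.9 |

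Table 1 is only a proxy for recruitment; it reports "Client volume in most recent month available of new and continuing injectable clients".

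**Step 4. Power.** Power = Φ[(0.075√(n/R) − z·s0)/s1]. Example, urban, rp 0.02, one-sided 5%: R = 1.436, n/R = 119.1, (0.818 − 0.584)/0.308 = 0.76, power 78%.

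| Provider ICC | 0 | 0.005 | 0.01 | 0.02 | 0.05 |
|---|---|---|---|---|---|
| Urban, one-sided 5% | 90% | 87% | 84% | 78% | 62% |
| Pooled, one-sided 5% | 96% | 94% | 92% | 89% | 77% |
| Urban, one-sided 2.5% | 82% | 78% | 73% | 65% | 48% |
| Pooled, one-sided 2.5% | 91% | 89% | 86% | 80% | 64% |

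These rows use equal loads, clinic ICC 0 and a normal reference. At one-sided 5%, a t reference with providers − clinics − 1 degrees of freedom (14 urban, 29 pooled) gives urban 87/83/80/73/58% and pooled 95/93/91/87/75%. A clinic ICC of 0.05 adds about 1 point.

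**Step 5. How far pooling protects the 90%.** One-sided 5%: (221/170.4 − 1)/18.15 = 0.016. With both kinds of uneven load: 0.297/22.9 = 0.013. One-sided 2.5%, equal loads: (221/211.6 − 1)/18.15, about 0.002.

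**The case against.** **The plan discloses the omission and hedges it, and its direction is right.** This stands. Some correlation does lower power and some does raise it. The documents contain no ICC, so nothing proves that the offset fails. There is even a mechanism for a sizeable clinic ICC: success is agreement with one facility nurse, who judges both cadres in that clinic. What is shown is how large the clinic ICC would have to be.

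**Provider variation may be small.** The protocol says "Jhpiego will certify that once trained, LHWs and LHVs are proficient in screening, counseling and administration of both forms of DMPA", and SAP IV points to standardised LHW training. This is a fair argument, but a different one. It supports a small loss of power; it does not produce an offset.

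**The ratio of 22 is specific to one layout.** This also stands. The protocol's site-selection text allows more sites to be added, which lowers the ratio, and it is about 18 for the pooled set. Uneven loads raise it.

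**Pooling is expected and recovers most of the loss.** Largely true at one-sided 5%, but pooling is conditional and the margin of safety depends on loads and alpha (Step 5).

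**The power figures do not describe the planned model.** Correct. They are risk-difference approximations, while SAP VIII fits a logit mixed model and reports an odds ratio. A plain Wald calculation is kinder (urban 94/92/89/84/71% over the same ICCs at one-sided 5%), although it does not reproduce 342.

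A reader might infer that 342 is miscalculated, that the trial is underpowered, or that the test will be invalid. The documents support none of these. The figure of 342 reproduces, the size of any loss rests on assumed ICCs, and the planned model contains both random effects.

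**Conclusion.** The concern holds in a limited form. The 90% applies to the urban set only if between-provider variation is negligible, and the offset given in its place is unsupported and demanding.

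The ratio of about 22 comes from the planned layout and needs no ICC value. The power losses do need one: an assumed provider ICC of 0.01 to 0.05 takes urban power from 90% to between 84% and 62%, under the conditions of Step 4. The issue matters mainly if the analysis is urban-only. At one-sided 5% with equal loads, pooling keeps power at or above 90% up to a provider ICC of about 0.016.

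That reassurance nearly disappears at one-sided 2.5%, which is what the two-sided 0.05 in SAP V.E implies for a non-inferiority test. This is a planning statement worth correcting; it does not threaten the validity of the result.

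**What to change.** 1. Settle the alpha first. The figure of 342 matches one-sided 5%, SAP V.E states two-sided 0.05, and the first Objective 1 table shell has a 90% interval column with a 95% interval footnote.
2. In protocol Sample size and SAP IV, replace the sentence about offsetting with wording such as: *The 90% power assumes negligible between-provider variation. Because each provider belongs to one cadre, provider correlation lowers power for the LHW-LHV comparison. No ICC estimate was available.*
3. Add a short table of power over a range of provider ICCs for the urban and pooled sets at the alpha adopted. State the number of clinics, the loads and the test. Either label it a risk-difference approximation or simulate it under the planned logit mixed model.
4. If the coefficient 21.8 is printed, give it only as the value for five urban clinics with equal loads, not as a general floor.
5. In SAP VIII, qualify the remark that the urban sample was powered by adding: *assuming negligible between-provider variation*.

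The cost is a sentence and a small table in two documents, one clause in SAP VIII, and the alpha decision. The downside is a less favourable stated power. No extra enrolment and no change to the analysis are proposed.
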